15.3 Vital Signs

Vital Signs (heart rate, systolic/diastolic blood pressure, respiratory rate and body temperature,) are assessed at Screening, Day 1, Day 2, Day 3, Day 10, Week 6, Week 13, Week 26, Week 39, Week 52 and the Safety Follow-up visit.

All summary tables will include vital signs recorded from baseline up to 30 days post treatment discontinuation.

The vital signs that are collected pre-dose and post-dose are:

- **Pre-dose:** body temperature, heart rate, systolic/diastolic blood pressure and respiratory rate.

Study 111-301 Statistical Analysis Plan

- **Post-dose:** heart rate and systolic/diastolic blood pressure only.
 - Day 1: 0-1 hr. (Q15min); 1-2hr (Q30min)
 - Day 2-3: 0-2 hr. (Q30min)
 - All other dosing visits: 0-1 hr. (Q30min)

The absolute values for pre-dose vital signs at each scheduled visit, and change from baseline in pre-dose vital signs at each scheduled visit will be summarized (n, mean, SD, median, 25th and 75th percentile, minimum, maximum) and presented by treatment group. Line plots will be generated which present the mean pre-dose absolute values (+/- SD) by scheduled visit for each treatment group.

In addition, for heart rate and systolic/diastolic blood pressure, pre-dose assessments, and change from pre-dose to multiple post-dose time points at each scheduled visit will be similarly summarized and presented by treatment group. Line plots will be generated which present the mean pre-dose and post-dose absolute values (+/- SD) by treatment group for each visit separately.

The percentage of subjects experiencing at least one instance of a decrease of 20% in diastolic blood pressure from pre-dose to post dose will be summarized [n(%)] by treatment group at Baseline, Day 2, Day 3, Day 10, Week 6, Week 13, Week 26, Week 39, and Week 52.

Shift tables (Diastolic BP <40mmHg, Diastolic BP \geq 40mmHg) from pre-dose to lowest post-dose value category (Diastolic BP <40mmHg, Diastolic BP \geq 40mmHg) will be generated by visit and at any time.

Shift tables (Diastolic BP <45mmHg, Diastolic BP \geq 45mmHg) from pre-dose to lowest post-dose value category (Diastolic BP <45mmHg, Diastolic BP \geq 45mmHg) will be generated by visit and at any time.

Shift tables (Systolic BP < (70mmHg plus 2 x Age), Systolic BP \geq (70mmHg plus 2 x Age)) from pre-dose to lowest post-dose value category ((Systolic BP < (70mmHg plus 2 x Age), Systolic BP \geq (70mmHg plus 2 x Age)) will be generated by visit and overall (overall will be the lowest overall post-dose value category at any time on study). Subject's age used in this calculation is the integer value.

PI

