9.12.6.9 Vital Signs, Physical Examinations and Other Observations Related to Safety

9.12.6.9.1 Vital Signs

Vital signs assessed pre-dose will include seated systolic blood pressure (SBP) and diastolic blood pressure (DBP) measured in mm Hg, heart rate in beats per minute, respiration rate in breaths per minute, and temperature in degrees Celsius (°C). All treatment visits have pre-dose vital sign assessments. Post-dose measurements include heart rate and BP. For all dosing visits, assessment frequency is detailed in Table 9.12.6.9.1.1 (see Schedule of Events, Table 9.1.1).

At Screening, after at least 5 minutes of rest, subject's BP is taken in sitting position. Then the subject will stand and BP will be taken again at approximately 1 and 3 minutes after standing. At other visits, vital sign measurements are taken once per time point in a sitting position after at least 5 minutes of rest. Heart rate should be taken at each time point that BP is measured. When blood samples and BP assessments are scheduled at the same time or within the same time window, BP should be measured before blood samples are drawn. If a BP measurement must be taken after a blood draw, ensure adequate analgesia for the blood draw and wait several minutes before measuring BP. Pre-dose vital signs should always be taken and recorded prior to pre-dose blood draw. Vital signs may be monitored more frequently or for longer duration post-dose as clinically indicated.

If a subject has symptoms potentially consistent with hypotension or a decrease in SBP of 20 mm Hg or more from pre-dose SBP, blood pressure and heart rate (HR) should be measured and recorded approximately every 15 minutes for the first hour and every 30 minutes thereafter until the systolic BP returns to pre-dose systolic BP (or within the normal range for this subject as defined by PI) and symptoms (if present) resolve. If the hypotension resolves within the first hour and returns to the normal range, additional BP monitoring as described above is not required. Detailed guidance for blood pressure measurements is provided in the Blood Pressure Instrument and Technique Guidelines.

	Study 111-301 Amendment 4	Page 75
---	---------------------------	---------

Table 9.12.6.9.1.1: Vital Sign Assessment Frequency

Vital Sign Assessment Frequency Pre-Dose		

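### The by-visit blood pressure incidence and lowest-value shift tables in SAP 15.3 rest on 6, 4 or 2 scheduled post-dose readings, so they can show a drop after Days 1-3 that comes from the schedule alone

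*SAP*

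**What the plan says.** SAP 15.3 sets three densities of post-dose blood pressure measurement: "Day 1: 0-1 hr. (Q15min); 1-2hr (Q30min"), "Day 2-3: 0-2 hr. (Q30min") and "All other dosing visits: 0-1 hr. (Q30min"). The vital sign tables in the protocol (Table 9.12.6.9.1.1 and the notes to Table 9.1.1) agree.

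The same SAP section then plans three kinds of by-visit output, split by treatment group:

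- The percentage of subjects with "at least one instance of a decrease of 20% in diastolic blood pressure from pre-dose to post dose", shown "at Baseline, Day 2, Day 3, Day 10, Week 6, Week 13, Week 26, Week 39, and Week 52".
- Diastolic shift tables with cut-offs of 40 and 45 mmHg, "from pre-dose to lowest post-dose value category", by visit and at any time.
- A systolic shift table with a cut-off of 70 mmHg plus twice the age. It "will be generated by visit and overall (overall will be the lowest overall post-dose value category at any time on study").

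Section 15.3 also plans descriptive statistics for the change from pre-dose at each post-dose time point. Protocol 9.12.6.9.1 adds unscheduled readings after symptoms or a systolic fall of 20 mm Hg or more, taken "approximately every 15 minutes for the first hour and every 30 minutes thereafter". The visible text of SAP 15.3 does not say whether these count in the incidence and shift tables.

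**The concern.** A percentage with at least one event, and a shift to the lowest value, are both worst-of-k statistics: they rise with the number of readings k even when nothing else changes. Here k falls from 6 to 4 to 2 as the study proceeds, and the visits are set out in one table.

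Protocol 7.5.2.2 names hypotension as a risk identified for BMN 111. These tables are a natural place for a reader to ask whether it eases after the first doses. Protocol 7.2.2 reports that exposure in Study 111-202 was similar after single and multiple doses and stayed consistent through 24 months, so a flat effect is plausible. In that case the tables would still suggest improvement after Day 3.

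**Working it through.** The plan states no figure for this point, so there is none to reproduce.

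**Step 1: count the scheduled readings** (SAP 15.3).

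- Day 1: 60/15 + 60/30 = 4 + 2 = 6 (15, 30, 45, 60, 90 and 120 minutes).
- Days 2 and 3: 120/30 = 4 (30, 60, 90 and 120 minutes).
- Day 10 and Weeks 6, 13, 26, 39 and 52: 60/30 = 2 (30 and 60 minutes).

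Reading Baseline in the incidence table as Day 1, the nine tabulated visits are one with 6 readings, two with 4 and six with 2.

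**Step 2: choose a model.** Let p be the chance that a single reading meets the threshold, the same for every reading and visit. Let ρ be the correlation between readings within a visit. With independent readings,

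P(at least one) = 1 − (1 − p)^k.

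At p = 5% this gives 1 − 0.95^6 = 26.5%, 1 − 0.95^4 = 18.5% and 1 − 0.95^2 = 9.75%.

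Independence is not realistic for the percentage fall, because all readings in a visit are compared with one pre-dose value. With equal, independent errors, two changes share the variance σ² of that value, out of a total variance of 2σ² each, so ρ is about σ²/2σ² = 0.5. Persistence within a visit pushes it higher. For correlated readings I used an equicorrelated normal model:

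P(at least one) = E[1 − (1 − q(Z))^k], with q(Z) = Φ((Φ⁻¹(p) − √ρ·Z)/√(1 − ρ)) and Z standard normal.

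**Step 3: results under a constant risk per reading.**

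| p | ρ | 6 readings | 4 readings | 2 readings | 6 v 2 | 4 v 2 |
|---|---|---|---|---|---|---|
| 5% | 0.5 | 18.6% | 14.4% | 8.8% | 2.1 | 1.6 |
| 5% | 0.7 | 14.8% | 12.0% | 8.0% | 1.8 | 1.5 |
| 5% | 0.9 | 10.0% | 8.8% | 6.8% | 1.5 | 1.3 |
| 10% | 0.5 | 32.1% | 25.9% | 16.8% | 1.9 | 1.5 |
| 10% | 0.9 | 18.2% | 16.3% | 13.1% | 1.4 | 1.2 |

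The ratios reach 1 only at ρ = 1.

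**Step 4: two arms.** Take constant risks of 10% on active and 5% on placebo, with ρ = 0.5. The difference is 32.1 − 18.6 = 13.5 points with 6 readings, 25.9 − 14.4 = 11.5 with 4 and 16.8 − 8.8 = 8.0 with 2. Within each visit the arms are compared like for like, but the risk difference still shrinks across visits.

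**Step 5: common readings only.** With the 30- and 60-minute readings alone, k = 2 at every visit. The expected percentage is then flat, for example 8.8% throughout at p = 5% and ρ = 0.5.

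**The case against.** The case on the other side has real weight.

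- *Consequence.* Protocol 14.4 makes the safety analysis descriptive. No visible test or decision rule uses a trend over visits, and both arms follow the same schedule. This stands and limits the stakes.
- *Existing mitigation.* The planned change from pre-dose by time point includes the mean, quartiles and minimum, so 30- and 60-minute changes can be compared across visits. SAP 15.1.2 adds exposure-adjusted hypotension event rates and a profile with time to first onset. This also stands, but none of these outputs gives matched incidence or matched category shifts.
- *The constant-risk model.* Protocol 7.2.2 gives a median Tmax of 5 to 16 minutes and a mean half-life of 24.4 to 27.0 minutes. If effect follows concentration, the 90-minute reading comes more than three half-lives after dosing (90/27.0 = 3.3), so the late readings may add less drug-related risk than the model assumes. The Day 1 reading at 15 minutes works the other way. The sizes are therefore illustrative.
- *Incomplete view.* A redacted block closes SAP 15.3, so the point covers the visible text only.

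A reader might infer that the apparent risk halves after Day 3. The figures do not support that: the step there is from 4 readings to 2, and it comes close to halving only if readings are independent (18.5% to 9.75%). A reader might also infer a spurious fade over the whole year, but all six visits from Day 10 to Week 52 have two scheduled readings.

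**Conclusion.** The point holds in a limited form. As SAP 15.3 is written, the by-visit incidence and lowest-value shift tables carry a downward step from Days 1-3 to later visits that reflects the number of readings. The direction follows from the schedule for any within-visit correlation below 1 when the risk per reading is constant. The size rests on the assumed 5% risk and correlation of 0.5 to 0.9: about 2.1 to 1.5 fold for Day 1 against later visits, and about 1.6 to 1.3 fold for Days 2-3 against later visits.

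It does not follow that the comparison of BMN 111 with placebo within a visit is biased, or that a real decline is absent; a real decline would add to the artefact. The tables at any time and overall pool visits and show no trend. This is a worthwhile correction to descriptive safety output, with no bearing on the efficacy conclusions.

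**What to change.** In SAP 15.3:

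1. Keep the planned tables that use all readings. Replacing them would lose the Day 1 reading at 15 minutes, the one nearest the quoted Tmax.
2. Add by-visit versions of the diastolic incidence table and of the diastolic and systolic shift tables, limited to the scheduled 30- and 60-minute readings that every dosing visit has.
3. Exclude event-triggered extra readings from the added tables.
4. Footnote the all-readings tables with the scheduled number per visit (6, 4 or 2).

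The SAP has a precedent: section 15.4 repeats its ECG summaries with post-dose assessments restricted to around the expected time of Cmax.

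The cost is some SAP wording and one extra set of tables from data already collected, with no change to study conduct. The matched version omits some Day 1-3 readings, which remain in the all-readings tables.

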**Study 111-301 Statistical Analysis Plan****15.4 Electrocardiogram**

Electrocardiogram (ECG) data are recorded at Screening, Day 1, Day 10, Week 13, Week 26, Week 39, Week 52, and at the Safety Follow-up visit.

ECG assessments are performed in triplicate on Day 1 (pre-dose and post-dose) and on study day visits (post-dose only). On days when PK samples are being drawn, post-dose ECGs should be performed within a 5-minute window prior to the 30-minute PK assessment (i.e. around the time of C_{Max}).

Summaries will be provided over all assessments, and repeated with the requirement that all post-dose ECG assessments should occur around the expected time of C_{Max}. The mean results of the ECG assessments meeting these criteria will be used for summaries and analyses.

All measures and means of the measures will be included in the listings.

The following ECG results will be summarized (n, mean, SD, median, 25th and 75th percentile, minimum, maximum) and presented by treatment group at Baseline (pre-dose and post-dose), and post-dose at Day 10, Week 13, Week 26, Week 39, Week 52:

- ECG Mean Heart Rate (beats/min)
- QT interval (msec)
- QTcB interval (msec)
- QTcF interval (msec)
- PR interval (msec)
- RR interval (msec)
- QRS Duration (msec)

The following endpoints will be summarized [n (%)] at Baseline, Day 10, Week 13, Week 26, and Week 52, and across all time points (using the highest mean QTc value), and presented by treatment group.

- Percentage of subjects with QTcB >450 to ≤480ms, >480 to ≤500ms, >500 msec
- Percentage of subjects with QTcF >450 to ≤480ms, >480 to ≤500ms, >500 msec

The following endpoints will be summarized [n (%)] at Baseline, Day 10, Week 13, Week 26, and Week 52, and across all time points, and presented by treatment group.

- Percentage of subjects experiencing at least one instance of a (decrease in mean heart rate from pre-dose baseline >25% and a mean heart rate <50 beats/min) post-dose.

Study 111-301 Statistical Analysis Plan

- Percentage of subjects experiencing at least one instance of an (increase in mean heart rate from pre-dose baseline >25% and a mean heart rate >100 beats/min) post-dose.

The following endpoints will be summarized [n (%)] across all time points and presented by treatment group.

- Percentage of subjects with a QTcF increase of 60ms from pre-dose baseline at any time
- Percentage of subjects with QTcF changes from pre-dose baseline of >30 and ≤ 60 msec, or >60 msec at any time
- Percentage of subjects with both an increase in PR interval from pre-dose baseline >25% and a PR>200 msec at any time.
- Percentage of subjects with both an increase in QRS from pre-dose baseline >25% and QRS >120 msec at any time

Listings will be provided, and ordered by treatment group, subject and visit:

- All ECG results.
- All ECG results for subjects with a QTc increase of 60msec from pre-dose Baseline.

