9.3.2 Exclusion Criteria

Individuals who meet any of the following exclusion criteria will not be eligible to participate in the study:

1. Have hypochondroplasia or short stature condition other than ACH (eg, trisomy 21, pseudoachondroplasia).
2. Have any of the following:
 - Hypothyroidism or hyperthyroidism.
 - Insulin-requiring diabetes mellitus.
 - Autoimmune inflammatory disease (including celiac disease, lupus (SLE), juvenile dermatomyositis, scleroderma, and others).
 - Inflammatory bowel disease.
 - Autonomic neuropathy.

B:OMARIN[®]	Study 111-301 Amendment 4	Page 54
-----------------------------	---------------------------	---------

3. Have a history of any of the following:
 - Renal insufficiency defined as serum creatinine > 2 mg/dl.
 - Chronic anemia.
 - Baseline systolic blood pressure (BP) < 70 millimeters of mercury (mm Hg) or recurrent symptomatic hypotension (defined as episodes of low BP generally accompanied by symptoms ie, dizziness, fainting) or recurrent symptomatic orthostatic hypotension.
 - Cardiac or vascular disease, including the following:
 - Cardiac dysfunction (abnormal echocardiogram [ECHO] including abnormal left ventricle [LV] mass) at Screening Visit.
 - Hypertrophic cardiomyopathy.
 - Pulmonary hypertension.
 - Congenital heart disease.
 - Cerebrovascular disease.
 - Aortic insufficiency or other clinically significant valvular dysfunction.
 - Clinically significant atrial or ventricular arrhythmias.
4. Have a clinically significant finding or arrhythmia on screening electrocardiogram (ECG) that indicates abnormal cardiac function or conduction or Fridericias corrected QT interval (QTc-F) > 450 msec.
5. Have an unstable condition likely to require surgical intervention during the study (including progressive cervical medullary compression or severe untreated sleep apnea).
6. Evidence of decreased growth velocity (AGV < 1.5 cm/year) as assessed over a period of at least 6 months or of growth plate closure (proximal tibia, distal femur) through bilateral lower extremity X-rays including both AP and lateral views.
7. Documented Vitamin D deficiency (concentration of blood 25-hydroxy-vitamin D < 12 ng/mL or < 30 nmol/L).
8. Require any investigational agent prior to completion of study period.
9. Have received another investigational product or investigational medical device within 6 months before the Screening Visit.

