**Study 111-301 Statistical Analysis Plan****5 GENERAL ANALYSIS CONSIDERATIONS**

The analyses described in this SAP are based on Amendment 4 of the protocol (dated 01-February-2019).

Individual subject data that is reflected in data summaries will be provided in **PI**. Unless otherwise specified, all **PI** will be by treatment group and ordered by subject number, where subject number includes the site number.

Summary tables and figures are provided by treatment group with no overall population column. There are certain exceptions (e.g. subject disposition, demographics, baseline characteristics and safety data) which are indicated in the relevant sections.

Baseline annualized growth velocity (AGV) is defined in Section 14.3.1. Baseline growth measures (other than AGV) and baseline weight are those assessed on Day 1 of dosing, regardless of timing relative to dosing. (Note: If no assessments are available, then the baseline assessment will be the last non-missing assessment prior to Day 1). All other baseline assessments are the last non-missing on-study 301 assessments prior to administration of study drug. Change from baseline is calculated as: [post-baseline value – baseline value]; Percent change from baseline is calculated as: ([post-baseline value – baseline value]/baseline value) x 100.

The Screening visit will not be presented in descriptive summaries over time. When the analysis windows have been applied (see Section 5.4), data collected at the screening visit may be included in the Baseline assessment. All assessments will be listed, but only those assessments assigned to visits according to the windows applied (see Section 5.4) will be summarized in tables or graphically. Exceptions to this are summaries of the worst post-baseline laboratory data in shift tables where all assessments are considered, and also the standing height assessments displayed in the spaghetti plots.

Unless otherwise specified, the number of subjects, mean, 25th percentile, median, 75th percentile and estimates of precision (e.g. SD, confidence interval) will be displayed to one more decimal place than the collected data. Minimum and maximum values will be presented to the same decimal places as the collected data. For summaries by visit, the number of subjects with non-missing observations (n) according to the analysis windows (see Section 5.4 for further details) at the derived visit will be presented.

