5.4 Visit Windows for Analysis

An assessment for a subject will be classified according to the study day of the assessment where it falls within a window.

Data in Study 111-901 for subjects who enrolled in Study 111-301 and are included in the corresponding analysis population will be used in efficacy summary tables and figures. The analysis visits and windows for assessments in Study 111-901 are defined in Table 5.4.1. Unless otherwise specified, only the derived visits listed in the table will be included in summary tables and figures.

Table 5.4.1: Visit Windows for Observed Assessments in BMN 111-901

Derived Visit	Target Day ^a	Analysis Window ^a
≥ 6 Months Prior	-182	> -364 to ≤ -182
≥ 12 Months Prior	-364	> -546 to ≤ -364

^a Target days and analysis windows are relative to the 111-301 Day 1 date defined in Section 5.3 above.

For each subject and growth measure in Study 111-901, the record closest to the target day within the analysis window will be retained for inclusion in summary tables.

Spaghetti plots of standing height and standing height Z-scores will include all measures recorded in Study 111-901 up to and including the “≥ 12 Months Prior” assessment without applying windows. This will allow for all subjects with height assessments ≥ 12 months prior to Day 1 to have at least one assessment included.

The analysis windows for assessments in Study 111-301 are defined in [Table 5.4.2](#). The analysis windows are designated for each scheduled visit and centered on a target day. If

	Study 111-301 Statistical Analysis Plan
---	--

there are two or more assessments within a designated window, the assessment that is closest to the target day will be used for analyses. If the two closest assessments to the target day are equidistant from the target day, the assessments taken on a scheduled visit per CRF page will be used. Unless otherwise specified, all analyses are based on derived visits.

Table 5.4.2: Visit Windows for Observed Assessments in 111-301

Derived Visit	Target Day ^a	Analysis Window ^a
Baseline		The last assessment prior to the first dose of study drug unless otherwise specified.
Day 1	Day 1	Day 1
Day 2	Day 2	Day 2
Day 3	Day 3	Day 3
Day 10	Day 10	Day 4 – 16 (-/+6)
Week 6	Day 43	Day 22 - 64 (-/+21)
Week 13	Day 92	Day 71 – 113 (-/+21)
Week 26	Day 183	Day 162 - 204 (-/+21)
Week 39	Day 274	Day 253 – 295 (-/+21)
Week 52	Day 365	Day 344 – 386 (-/+21)

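### The all-time-points QTc category row in SAP 15.4 is not limited to post-dose ECGs, so a pre-dose value alone can place a child in it; the effect is small and confined to descriptive safety tables

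*SAP*

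**What the plan says.** SAP 15.4 (Electrocardiogram) plans two absolute-threshold summaries: "Percentage of subjects with QTcB >450 to ≤480ms, >480 to ≤500ms, >500 msec" and "Percentage of subjects with QTcF >450 to ≤480ms, >480 to ≤500ms, >500 msec". Both are given by treatment group "at Baseline, Day 10, Week 13, Week 26, and Week 52, and across all time points (using the highest mean QTc value".

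Three places in the SAP bear on what Baseline means here:

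- Section 5, the general rule: "All other baseline assessments are the last non-missing on-study 301 assessments prior to administration of study drug".
- Section 5.4, Table 5.4.2: "The last assessment prior to the first dose of study drug unless otherwise specified".
- Section 15.4 itself, for the continuous ECG results: "presented by treatment group at Baseline (pre-dose and post-dose), and post-dose at Day 10, Week 13, Week 26, Week 39, Week 52".

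On timing, 15.4 states that "ECG assessments are performed in triplicate on Day 1 (pre-dose and post-dose) and on study day visits (post-dose only". The Day 1 pre-dose triplicate is therefore the only planned ECG between screening and the first dose.

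The entry limit on QTc is exclusion criterion 4 in Protocol 9.3.2. It concerns the screening ECG and names "Fridericias corrected QT interval (QTc-F) > 450 msec", alongside clinically significant findings. It sets no QTcB value.

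**The concern.** An overall worst-value row in a safety table is normally read as the number of children who reached a threshold after exposure. If the worst value may come from an ECG taken before the first dose, the row mixes pre-exposure values with values on treatment.

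Two things follow. Children are added to both arms for a reason unrelated to the drug. And if the drug does raise QTc, the placebo arm gains more of these children than the active arm, because fewer active-arm children are left without a post-dose exceedance. The contrast then moves toward no difference.

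QTcB is the more exposed measure. It has no explicit entry limit, and the categories of change from pre-dose baseline in 15.4 are defined for QTcF only, so the all-time-points row is its only planned cumulative outlier summary.

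**Working it through.** The plan attaches no figure to this row, so there is nothing to reproduce. The check is of wording first, then of size under stated assumptions.

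**1. Is the pre-dose ECG in the row?** Under Section 5 and Table 5.4.2, Baseline is the last pre-dose assessment. Under the usage for continuous results in 15.4, it covers both pre-dose and post-dose ECGs. On all three, the pre-dose value is among those from which the highest is taken. 15.4 also repeats its summaries with ECGs restricted to around the expected Cmax, but that restriction applies to post-dose ECGs only and does not remove the pre-dose one.

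**2. How do the SAP's other worst-value summaries compare?**

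- Heart-rate outliers (15.4): limited to post-dose.
- Laboratory shift tables (15.2): worst post-baseline value.
- Overall systolic blood pressure row (15.3): lowest post-dose value.
- QTc categories, overall row (15.4): no limit stated.

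**3. Can a pre-dose value above 450 ms occur?** Yes. Criterion 4 does not cap QTcB, and the Day 1 pre-dose ECG is a later recording than the screening ECG, so QTcF can exceed 450 ms then too, though less readily.

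**4. How large is the effect?** Assumptions, none from the documents:

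- chance r that a single ECG exceeds the threshold: 2%, 5% or 10%
- within-child correlation ρ: 0.3 or 0.6, in a normal random-intercept model
- drug shift d: 0 or 0.5 SD, post-dose only
- post-dose ECGs k: 4 (Day 10, Weeks 13, 26 and 52, the later visits in the list) or 6 (adding Day 1 post-dose and Week 39)

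The 55 children per arm come from SAP 4.5.

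With t = Φ⁻¹(1 − r) and u standard normal:

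- Row limited to post-dose: P = 1 − E[ Φ((t − d − √ρ·u)/√(1−ρ))^k ]
- Row as worded: the same, with the extra factor Φ((t − √ρ·u)/√(1−ρ)) inside the expectation for the unshifted pre-dose ECG.
- Children counted only through the pre-dose ECG: 55 × (row as worded − row limited to post-dose).

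Three of the 12 scenarios, by numerical integration. Each cell runs from post-dose only to as worded:

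| r, ρ, k | No shift | Extra per 55 | 0.5 SD shift | Extra per 55 | Arm difference, points |
|---|---|---|---|---|---|
| 2%, 0.6, 6 | 7.70% → 8.48% | 0.4 | 19.45% → 19.74% | 0.2 | 11.75 → 11.26 |
| 5%, 0.3, 4 | 16.35% → 19.33% | 1.6 | 35.58% → 37.24% | 0.9 | 19.23 → 17.91 |
| 10%, 0.3, 4 | 29.52% → 34.05% | 2.5 | 53.29% → 55.41% | 1.2 | 23.77 → 21.36 |

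Example, second row: 55 × (0.1933 − 0.1635) = 1.6 children. The risk ratio goes from 35.58/16.35 = 2.2 to 37.24/19.33 = 1.9.

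Over all 12 scenarios:

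- Extra children per arm with no shift: 0.4 to 2.5, which is about 6–17% of those in the row.
- Extra children in the shifted arm: 0.2 to 1.2.
- Loss in the arm difference: about half a point to 2.4 points. The risk ratio is lower in every scenario.

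**The case against.** The strongest counter-argument is about the word Baseline. When 15.4 means the pre-dose value it often says so (the heart-rate, QTcF-change, PR and QRS items). The sentence after the QTc categories uses the same visit list for heart-rate changes from pre-dose baseline that occur post-dose, and there Baseline can only be Day 1 post-dose. The diastolic blood pressure summary in 15.3 uses Baseline in the same way, and Table 5.4.2 allows for exceptions. This stands as evidence of inconsistent usage. It does not settle the QTc row, because the SAP never states the Day 1 post-dose meaning there and its general definition points the other way.

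A reader might infer that the SAP reports pre-exposure values as on-study or treatment-emergent events. The documents do not support that: the row is labelled as covering all time points and claims no more.

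A reader might also infer that a QTc signal could be hidden. That is not supported either. No post-dose exceedance is dropped. Baseline has its own column. The later visits shown separately carry post-dose ECGs only. QTcF changes from pre-dose baseline are tabulated at any time, and all ECG results are listed. What these outputs lack is a table showing how many children in the overall row were outliers only before dosing; that would have to be rebuilt from the listings.

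Finally, no risk ratio or test is planned for this table, Protocol 14.4 calls the safety analysis descriptive, and with 55 per arm a shift of one or two points is well within sampling noise. All of this stands and limits the weight of the point.

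**Conclusion.** The point holds as a wording gap with a small effect. As written, the overall QTc category row is not limited to post-dose ECGs, and a child whose only value above 450 ms preceded dosing would be counted. The consequence falls mainly on QTcB; QTcF is partly protected by the screening exclusion and by its change-from-baseline categories.

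The size, at most two or three children per arm, rests wholly on the assumed exceedance rates, correlation, number of ECGs and shift. The direction is firmer: under a true upward shift, including the pre-dose value moves the contrast toward no difference, and randomisation does not remove that. The issue is limited to descriptive safety reporting. It does not touch the primary or key secondary analyses or the type I error.

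**What to change.** In SAP 15.4, reword the overall row of the QTcB and QTcF categories to: across all post-dose time points (highest post-dose mean QTc, including Day 1 post-dose). Keep the pre-dose Baseline as its own column and label it pre-dose.

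In the same edit, say whether the Week 39 and Safety Follow-up ECGs count toward the overall row. Both are recorded under 15.4, but neither is in the visit list for these categories.

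A cross-tabulation of worst post-dose category against pre-dose baseline category would be informative, especially for QTcB, but is optional.

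The cost is one clause of SAP text and one filter in the ECG table program. No new data are needed.
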